**Data must be kept for seven years after the study has been completed.**

### Potential Risks/Adverse Events

1. Describe reasonably foreseeable risks or discomforts to the subjects and steps to minimize risks.  
**The study involves minimal risks and steps will be taken to mitigate these risks. Risks include: soft tissue infection, breast implant infection, decreased quality of life, breach of confidentiality. Infection risk may be higher, lower, or the same in those who allowed to shower with drains in place compared to those not allowed to shower. There is a lack of literature to support increased risk of infection with showering with JP drains in place. Timing of showering is ultimately surgeon dependent. Regardless, this risk will be mitigated by continuing with sterile surgical technique with proper prepping and draping of the patient as well as sterile placement of drain tubes intra-operatively. Patient's will also be instructed to not soak in water, such as in a bath tub. Rather, they will be instructed to shower and let water run over the drain tube sites. Patients will be immediately treated if there any signs of infection. In terms of decreased quality of life, patients who will not be allowed to shower until drain tubes are removed will be allowed to sponge bath to help mitigate any discomfort. The final risk is possible breach of confidentiality. These risks will be minimized by de-identification of data collected on a separate file, a link between randomly assigned number and identifiable data will be listed. All data collected will be secured on a password protected excel spreadsheet. No persons outside those listed. Accidental removal of a surgical drain is not increased by this study. It is part of our routine care to suture the drain tubes to the skin. Accidental dislodgement of drains is an extremely rare event and is part of the normal post operative surgical risks.**
2. Describe any stopping rules.  
**We would immediately withdraw patients per their request. We would also stop the study all together if there was a clear statistical benefit in one of the study arms.**
3. Include the plan for reporting unanticipated problems or deviations. This plan must include a five-day reporting requirement to the IRB once becoming aware of an event.  
**Patients will be educated on the signs concerning for SSI and appropriate protocol for reporting any concerns. This will consist of calling the UMHC PRS clinic to schedule immediate follow-up to be assessed for SSI. If a patient is found to have a**

**SSI they will be treated with appropriate antibiotics. The IRB office will immediately be notified within the five day reporting requirement.**

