### Research Objectives/Background

1. Include primary, secondary, and exploratory objectives.  
**Primary goal: to evaluate whether allowing showering after a certain number of days post breast reconstruction has an effect on the infection rate**  
**Secondary goal: to evaluate whether allowing showering after a certain number of days post breast reconstruction has an effect on the quality of life of patients**
2. Include background and rationale for initiating the study. Includes pre-clinical and clinical data, current experiences with procedures, drug, or device, and any other relevant information to justify the research.  
**Currently, there is a lack of consensus on best practices regarding showering with drains in place following first stage breast reconstruction. There is anecdotal concern for an increased risk of Surgical Site Infection (SSI), but the current literature to support this is lacking. There is also some evidence that showering with drain tubes in place has no increase risk of infection. It is not known whether showering with drain tubes decreases the risk of SSI. Surgical drains can remain in place upwards of two to three weeks in the postoperative period. The recommendation not to shower until drain removal can present a significant challenge for patients resulting in distress and decreased quality of life. Our study will assess the infection rates in patients allowed to shower at 48 hours postoperatively compared to those not showering until drains are removed. Our hypothesis is that this study will reveal no difference in the rates of SSI and improved quality of life in patients who are allowed to shower with drain tubes in place.**

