### Number of Subjects

1. Include anticipated enrollment number in this study. Include a break-down in numbers if there is more than one subject population.  
**Our goal is to achieve an  $n$  of 100 with 50 patients allocated to the experimental arm (showering at 48hrs) and 50 allocated to the control (current standard of care).**
2. Include statistical analysis or other justification for the number of subjects enrolled.  
**An  $n$  of 100 provides us with adequate power for a statistically significant difference between subject arms to be detected if one is present.**

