### Study Procedures/ Design/Treatment Plan

1. Include study procedures/design/plan; include the sequence and timing of study procedures (distinguish research procedures from those that are part of routine care). Include study duration and number of study visits required.  
**Study will last 90 days. Patient's will be admitted to the hospital following surgery if the reconstruction takes place immediately following mastectomy. If the reconstruction does not occur at the same time as mastectomy, patients are not admitted. This is part of our routine care. Regardless, they will be evaluated on post operative day one. Following the initial post operative day one visit, patient's will be evaluated on a weekly basis for 90 days. Vitals will be taken at the visits, and routine physical examination (including evaluation for surgical site infection) will be performed. Patient reported outcomes will be obtained at these visits as well. We will also ask patients if they have been showering or not and if so how often. This will be documented. For example: patient evaluations will be as follows:**
  - One-month preoperative visit
  - Day of surgery
  - Post Operative Day one evaluation (In the hospital or clinic)
  - Clinic Visit 1: One week after surgery
  - Clinic Visit 2: Two weeks after surgery

**These visits will not differ from our routine care. At the conclusion of 90 days patients will receive a survey asking if drain care and the ability or inability to shower with drain tubes in place adversely affected their quality of life.**

2. Blinding, including justification for blinding or not blinding the trial. Describe unblinding procedures.  
**The study will not be blinded. Participants will be randomly assigned to treatment arm. Researchers and patients will know which arm they are assigned to.**
3. Justification of why participants will not receive routine care or will have current therapy stopped.  
**The goal of the study is to determine if there an effect on infection rate with allowing patients to begin showering 48 hours after surgery rather than waiting to shower until drains are removed. There is no definitive literature on this, and the care of surgical drains is ultimately decided by the surgeon. There is currently no defined standard of care regarding showering with surgical drains in place.**

4. Definition of treatment failure or participant removal criteria.  

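### The rule to stop the whole study for a statistical benefit sets no limit on looks and no threshold that protects the type I error

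*Protocol*

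**What the plan says.** The stopping rule is in the Protocol, Potential Risks/Adverse Events, item 2. After withdrawal at a patient's own request, it gives one study-level rule: "We would also stop the study all together if there was a clear statistical benefit in one of the study arms". It does not name the outcome, the test, the threshold, the number or timing of comparisons, or who reviews the data apart from the study team, and it points to no other document for these.

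Three other places bear on it:

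- Study Procedures/Design/Treatment Plan, item 2, makes the study open label: "Researchers and patients will know which arm they are assigned to". Item 1 of that section has patients examined, including for infection, throughout follow-up: "patient's will be evaluated on a weekly basis for 90 days".
- Research Objectives/Background sets the primary goal: "to evaluate whether allowing showering after a certain number of days post breast reconstruction has an effect on the infection rate".
- Number of Subjects plans a total "of 100 with 50 patients allocated to the experimental arm (showering at 48hrs) and 50 allocated to the control". The justification is only that this number "provides us with adequate power for a statistically significant difference between subject arms to be detected if one is present". It gives no alpha, rates or effect size and makes no allowance for interim testing.

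**The concern.** A rule that stops the study when a benefit appears can work only if someone compares the arms before all 100 patients are in. Each comparison is another chance for a random imbalance to look like an effect. If the bar is ordinary significance each time and the final test also uses full alpha, the overall false-positive rate exceeds that of a single test.

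Few events would be needed. With uncorrected chi-square, 4 infections against 0 gives p = 0.025 at 10 per arm and p = 0.037 at 25 per arm.

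A chance cluster of this kind could end the study and be reported as showering causing or preventing infection. The protocol hopes to inform practice, so the error could carry in either direction. The reported p-value and confidence interval would ignore the looks, and the estimate at an early stop would be exaggerated. With no true difference, 10% SSI and chi-square, the mean absolute difference among significant results is about 14 percentage points with a single test and 19 with five looks.

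**Working it through.** **Inputs from the protocol.** 50 per arm; a binary infection outcome; open label. The rule applies to benefit in either arm, and the risk section allows for either direction ("Infection risk may be higher, lower, or the same in those who allowed to shower with drains in place"), so I read the comparison as two-sided.

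**Assumptions, because the protocol gives no figures.** Nominal two-sided 0.05 at every look; the same true SSI rate in both arms, from 5% to 20%; patients accruing in pairs with outcomes known; looks equally spaced, with the last at 50 per arm. Continuous means a look after every pair from 10 per arm onward, which is 41 looks.

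**The plan's own figure.** The 100 cannot be reproduced, because no design inputs are stated. No alpha is given from which to start.

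**Step 1, benchmark under normal theory.** With K equally spaced looks, each rejecting at |z| ≥ 1.96, the overall type I error is 5.0% (K = 1), 8.3% (2), 14.2% (5) and 19.3% (10).

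**Step 2, the binary outcome at 50 per arm.** With a and b infections among n per arm, pooled rate p = (a + b)/(2n), the uncorrected statistic is z = (|a − b|/n) / √(2p(1 − p)/n). For 4 against 0 at n = 10: p = 0.20, z = 0.40/√0.032 = 2.24, two-sided p-value 0.025. I enumerated the joint distribution of the two infection counts pair by pair and removed, at each look, the paths with a p-value of 0.05 or less. The removed probability is the overall false-positive rate. Simulation with 100,000 runs agrees to within 0.4 percentage points.

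| Test, true SSI rate | 1 look | 2 looks | 5 looks | 10 looks | Continuous |
|---|---|---|---|---|---|
| Chi-square, 5% | 4.3% | 5.6% | 7.5% | 8.6% | 9.5% |
| Chi-square, 10% | 5.1% | 8.3% | 11.9% | 14.7% | 16.6% |
| Chi-square, 20% | 5.2% | 8.9% | 13.2% | 18.4% | 20.0% |
| Fisher, 5% | 0.7% | 0.8% | 1.0% | 1.1% | 1.3% |
| Fisher, 10% | 1.8% | 2.4% | 3.6% | 4.4% | 5.4% |
| Fisher, 20% | 2.8% | 4.4% | 6.6% | 8.3% | 10.2% |

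The rate rises along every row. Whether it passes 5% depends on the test, the SSI rate and the number of looks.

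**Step 3, with a controlled boundary.** One interim look at 25 per arm with Fisher p ≤ 0.001, then a final chi-square test at 0.05, gives an overall rate of 4.3%, 5.1% and 5.2% at 5%, 10% and 20% SSI. These equal the single-test values to the decimal shown. For two equally spaced looks under normal theory, the O'Brien-Fleming nominal levels are about 0.005 and then 0.048.

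**Step 4, what the 0.001 boundary gives up.** At 25 per arm it is crossed only by splits such as 0 against 10, 1 against 12 or 2 against 14 infections. The chance of crossing is about 2% when the true rates are 10% and 30%, and about 12% when they are 10% and 40%.

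**The case against.** **Left to the analysis plan.** Looks and boundaries are often specified in a statistical analysis plan, which may exist here but is not shown. That would answer a complaint that detail is missing. It does not answer this one: the protocol itself states an operative rule for ending the study, in open-ended terms, and defers nothing.

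**No repeated testing is written down.** This stands. A reader might infer that the protocol prescribes repeated tests of SSI at 0.05. It does not: it schedules no looks and states no alpha or test. The weekly visits are patient examinations, and knowing the allocation is not the same as testing between arms each week. The reference to statistical significance under Number of Subjects justifies the sample size and is not a stopping threshold. The word clear might also mean something stricter than 0.05, although nothing defines it. The inflation is therefore conditional on more than one look at an unadjusted level.

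**Chi-square suits the early looks poorly.** This also stands. At 10 per arm, the expected number of infections per arm is 10 × 0.10 = 1 at a 10% rate and 10 × 0.20 = 2 at a 20% rate, and many analysts would use Fisher's exact test. A reader might infer that the error exceeds 5% whichever test is used. With Fisher it does not do so materially at SSI rates of 10% or less, even with continuous looks. Nor is the excess under chi-square uniformly large: at 5% SSI with five looks, it is just under 2.5 points above nominal. The protocol does not commit to either test.

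**Infection is also a safety outcome.** A strict boundary that barred all other comparisons would stand in the way of safety oversight. This is right, and the remedy must be limited to statistical stopping.

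**Conclusion.** The point holds in conditional form. The protocol commits unblinded researchers to end the study on an undefined statistical benefit, with no cap on between-arm looks and no alpha-preserving threshold. That looks increase the false-positive rate is certain; by how much is not, because alpha, test, SSI rate and number of looks are all assumed.

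If clear is read as two-sided 0.05 and uncorrected chi-square is used, the rate at 10% SSI goes from about 5% to 8%, 12% and 17% with two, five and continuous looks. At 20% SSI it goes to about 9%, 13% and 20%. At 5% SSI it goes from about 4% to 7.5% with five looks and 9.5% with continuous looks. With Fisher's exact test, it stays at or below about 5% for SSI of 10% or less and reaches about 6.6% (five looks) to 10% (continuous) at 20% SSI.

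The rule should be defined before data accrue. The documents do not show that the trial has made, or plans, any particular number of looks.

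**What to change.** Replace the sentence on stopping the whole study with a rule that names SSI as the outcome, fixes the number and timing of between-arm looks, and states an alpha-controlling boundary. Either of these would do:

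- one look when 50 patients have completed 90 days, stopping only at two-sided p ≤ 0.001 (Haybittle-Peto), with the final test at 0.05;
- the same single look with O'Brien-Fleming levels of about 0.005, then 0.048 at the end.

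Alternatively, state that there will be no early stop for a statistical difference, with one test at the end.

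Add that the rule governs statistical stopping for a between-arm difference only. It should not bar safety review of accumulating infections, and withdrawal on request and reporting of each SSI to the IRB stay unchanged.

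The cost is a short protocol amendment, with no extra patients or visits. The real price is that a statistical early stop becomes unlikely unless the difference is very large. Under the 0.001 rule at 25 per arm, the chance is about 2% for true rates of 10% and 30%, and about 12% for 10% and 40%. The team should accept this knowingly, which is a further reason to keep safety review separate.

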### **Anticipated Benefits**

1. Include both direct and indirect benefits for either the individual or society.  
**Direct benefits include better understanding factors that contribute to SSI in the postoperative period following first stage breast reconstruction. Indirect benefits include the ability to change current standard practice regarding showering with drains to improve patient quality of life.**

### **Compensation**

1. Describe the amount, method, and timing of disbursement. Compensation can include checks, cash, gifts, extra/course credit, etc.  
**No compensation will be provided. Patients will be recruited for this study on a volunteer basis.**

### **Costs**

1. Detail costs of study procedures, drugs, biologics, or devices and identify who will cover the cost.  
**There is no attributed cost for study procedures. We will be implementing two treatment arms: showering after 48 hours post operative with JP drains in place vs showering after JP drain removal. Survey will be voluntary**

### **Multiple Sites**

1. Specify who is the lead site and describe the roles of each site in the study.  
**UMHC PRS Clinic is the primary and only site being included in this study.**
2. Indicate that all required approvals are already in place or will be in place at each site prior to project implementation. If the study will utilize a reliance agreement or a single IRB, please describe which institution(s) will be relying on another IRB for review, and which institution will be responsible for the IRB oversight of the relying IRB(s).  
**A single IRB will be utilized for this study.**
3. Describe the plan that is in place to manage information obtained from multiple sites that may be relevant to the protection of human subjects such as reporting unanticipated problems, protocol modifications, and interim results.  
